a) Characterizing the post-acute stage. There is very limited knowledge of the post-acute stage of NMDARe; it is even unclear if immunotherapy or only symptomatic treatment is needed (antibody titers are not useful for these decisions). In a pilot prospective study we found an array of previously under-recognized symptoms (sleep and psychiatric alterations, inappropriate behavior, memory and cognitive deficits) [9]. Some patients were re-admitted to psychiatric facilities and we are aware of patients prosecuted for inappropriate social behavior. In this study, which also included a group of persons with schizophrenia (SCZ) and a group of healthy participants, we found that the cognitive and psychiatric symptoms of the post-acute stage of NMDARe resembled those of patients with stabilized SCZ. Despite sustained improvement in psychiatric scales, longitudinal follow-up showed that the cognitive deficits of NMDARe, but not those of SCZ, improved initially but stagnated at ~6 months. This represents an opportunity for targeted treatment that we will address in this proposal. The mechanisms underlying these alterations are unknown. Psychophysical testing showed that patients with NMDARe or SCZ had intact precision in a working memory (WM) task but a strong reduction of serial dependence (which is the influence of previous experiences in performing the WM task [17]). In animal models serial dependence of similar WM task relates to synaptic plasticity [18], suggesting a role for NMDAR-dependent short-term synaptic potentiation in NMDARe.[17] In longitudinal studies, the WM alteration of serial dependence along with other symptoms improved gradually in NMDARe towards the value of healthy controls. Additionally, in the same pilot study, we identified that patients with NMDARe had changes in the slope of individual slow-waves during deep sleep (postulated to reflect synaptic strength).

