4.1 Primary and secondary variables

Description of primary and secondary variables by specific objectives:

1. Clinically characterize the post-acute stage of NMDARe, provide tools to remotely follow cognitive, behavioral and psychiatric deficits, and assess the impact of a cognitive rehabilitation program.

1.1 General clinical data that will be obtained at each visit from all patients include (all primary variables): age, gender, vision condition, handedness, general medical history, allergies, description and duration of symptoms related to NMDARe, treatments, functional status according to modified Rankin Scale (mRS).

1.2 Presential neurocognitive assessment (primary variables): general neurological examination and a battery of 16 tests (with standardized versions adapted for adults and children) encompassing 8 cognitive domains: intelligence quotient, working memory, learning and memory, psychomotor speed, executive functions, selective and sustained attention, language, visuospatial perception.

1.3 Presential psychiatric assessment (primary variables): Structured clinical interview to assess the presence of psychiatric disorders following DSM-IV-TR guidelines (SCID-I for adults and K-SADS-PL for school-age children, psychotic symptoms (Positive and Negative Syndrome Scale, symptoms of depression (Hamilton Depression Rating Scale), symptoms of mania (Young Mania Rating Scale), Global Assessment of Functioning Scale or Children's Global Assessment Scale.

1.4 Remote cognitive assessment (secondary variables): customized panel of 8 tests for 6 cognitive domains covering working memory, learning and memory, psychomotor speed, executive functions, selective and sustained attention. It will be performed using one of the most validated cognitive research software available (CANTAB:

https://www.cambridgecognition.com/cantab/). Our group already has experience working

with it, and our feedback from patients is usually satisfactory. During presential visits, patients will be trained to use the online platform, and once at home they will run the exercises on an iPad that they will borrow from us and return to us after the tests (we will provide a courier service, and the iPad will have all the necessary software installed, ready to use). An experienced neuropsychologist from our team will guide them through the process and supervise the timings.

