Left over samples of blood and CSF that were obtained and stored during the acute stage of the disease (by the time of symptom onset and local hospital admission) will be obtained from the core laboratory (CBD) for patients seen at our center or will be sent to our center from the referring doctors. The diagnosis of NMDARe requires demonstration of antibodies in CSF (serum can be negative); thus, initial CSF studies form part of standard of care in this disease. For the current study, the left-over routine care serum and CSF samples from the 20 recruited patients will be used after their informed consent. For patients followed at our institution, we will take advantage of a regular follow-up visit to inform about the study and obtain their consent. For patients cared for at other hospitals, the referring doctors will explain the possibility of participating in the current study and, if the patients consent, we will contact them to provide further explanations and in such case obtain the informed consent. These acute samples will be tested for the indicated (see below) biomarkers of autoimmunity, inflammation, and neuronal injury. We are a referral center for the diagnosis and study of this disease, and therefore we have ample experience in receiving and handling the samples.

During the post-acute stage (by the time that patients will come to Hospital Clínic de Barcelona), blood and CSF samples will be obtained for identical studies as those performed in the acute stage serum and CSF samples. Two lumbar punctures will be performed, after informed consented, one at the first presential visit (V1) and the other at the last presential visit (V3). Patients will be given the option to opt out of the two spinal taps. Based on the recently published pilot study and extensive experience with the disease, all patients at V1 have cognitive and psychiatric alterations and most still have residual deficits at V3; thus, the CSF studies are important for investigations on biomarkers of disease severity, outcome and prognosis, and for better optimization of therapeutic options.

In addition to human studies, the current project includes an experimental animal model of

NMDARe using active immunization with the NMDA receptor. Thus, human biological samples will not be used in this experimental animal model (detailed later).

6. Selection of participants

Study group

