The general outline of the study including presential and remote visits and cognitive training is summarized in **Figure 1**; and the evaluations and tests during each of the three presential visits (except CSF studies that will be performed only in the first and last visit) are shown in **Figure 2**. A more detailed description of tests, interventions and calendar of the studies is provided following both figures.

Figure 1: Outline of presential and remote visits and cognitive training

V1, V2, V3= visitas presenciales; V1= 1st visita de estudio; V2= seguimiento a los 6 meses; V3= seguimiento al 1 año
A→D= entrenamiento cognitivo; A,B= 2 sesiones/semana; C= 1 sesión/semana; D= 1 sesión/2 semanas
R₁, R₄, R₅ = evaluación cognitiva remota (estudio comparativo con V1, V2 y validación de estudio remoto)
R₂, R₃, R₅ = evaluación psiquiátrica remota R₂, R₃= dispositivos portátiles (Memoria, EEG/sueño); s= semanas

Figure 2. Schedule for each presential visit

Presential visits

This study includes a total of 3 presential visits during 1 year. After hospital discharge, patients will come to our center ~2-5 months after disease onset for the **first (baseline) presential study visit (V1)** and for **follow-up visits 6 months (V2)** and **12 months (V3)** after V1. Each visit will consist of 2 days and 1 night admission at HCB (children, adults) during which they will undergo clinical examinations and tests according to a pilot study, including: neuropsychiatric and cognitive assessments, psychophysical studies, MRI, v-PSG, EEG. At V1 and V3, patients will undergo blood and CSF studies (variables 2.1, 2.2 and 2.3 will be analyzed in these paired blood/CSF samples and will be compared with those from the acute stage).

- Presential standard neuropsychiatric examinations and cognitive assessments will be conducted as per routine clinical practice and with a reported panel of neurological functional, cognitive and psychiatric tests (variables 1.1, 1.2 and 1.3). Total time ~4h spread over 3 sessions (the exact timetable can be adapted to patients' preferences and the length of the interviews will vary according to patients' clinical status; the times are indicative and are overestimated to be sure). These clinical evaluations will take place in the same room where the patients will sleep, and patients will have enough pauses in between to rest, eat/drink and go for a walk outside the hospital with their relatives.

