Remote cognitive rehabilitation program will be performed through an online validated platform (Guttmann Neuropersonal Trainer [GNPT]: https://gnpt.es/) run by our team. This is a Sanitary Product with CE certification (Producto Sanitario RPS/430/2014; International Patent [PCT/ES2008/00677]) and here will be used within its approved indications. The rehabilitation program will increase in difficulty and decrease in frequency during the first year of follow-up (V1-V3).

Patients/families will be instructed to perform remote cognitive rehabilitation during the presential visits. Patients will be able to use their personal computer and access via an available link and a user code the GNPT platform. In case that they do not have easy access to adequate equipment to access the platform, we will provide the iPad tablet with all the necessary software installed and ready to use to support their training. The indicated frequency of cognitive training is based on results of a recently published pilot study in which patients were followed with only presential visits (no remote visits or cognitive training was provided). The study showed that a slow progressive cognitive improvement occurred in most patients during the 1 year follow-up. However, the improvement was more marked during the first 6 months compared with the last 6 months. This finding suggested that intensive cognitive training (particularly during the first 6 months) could

accelerate recovery and improve outcome. Accordingly, for the current study patients will undergo cognitive rehabilitation twice per week for the first 6 months and once per week for the last 6 months. Similar programs are currently used by our team for patients with multiple sclerosis (along with collaborations with Institute Guttmann, Barcelona). Remote cognitive sessions will take ~45-60min.

Experimental mouse model of NMDARe

These studies are separate from the human studies. The animal study protocol is currently under revision by the CEEA-UB with registration number 420.22, already pre-approved. As indicated, no human biological samples will be used for the experimental animal model. Of note, although the animal studies are independent of human studies, the running in parallel of both sets of investigations will inform on the mechanisms of the disease and may have future treatment and prognostic implications.

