8.2. Statistical analyses

For human studies, we will analyze differences in cognitive and psychiatric variables between and within groups (newly recruited NMDARe patients and those from the pilot study) in the longitudinal follow-up using multilevel linear mixed-effect models, adjusting for group, age, sex, and socioeconomic status to control for possible confounds. Lme4 R package will be used to fit LME models, and residual plots will be used to validate them. Comparisons will be done with emmeans library and Tukey method for post-hoc correction for multiple testing. The global tendency of recovery of cognitive deficits in NMDARe (proportion of patients compared to the general population in each domain) will be assessed with the Cochran-Armitage test for trend; other comparisons within NMDARe will be done with Wilcoxon signed-rank and McNemar's tests. The patient behavioral, PSG and EEG data will be analyzed with linear regression using multiple regressors (task parameters, fraction of NREM N3, disease condition, with/without remote training, etc.). All analyses will be addressed considering a two-tailed type I error of 5% with statistical significance set at p-value <0.05, using SPSS (IBM Corp, Armonk, NY) and R package (Vienna).

For animal behavior studies with multiple determinations in time (e.g., new object recognition) we will use the double variance analysis (ANOVA). For behavior studies with a single determination in time (e.g., depressive behavior; "tail suspension") we will use the simple ANOVA. Electrophysiological studies (long-term potentiation) will be analyzed with double ANOVA. In all experiments, the post-hoc analysis will use the Bonferroni correction for multiple tests. A value of p <0.05 will be considered significant. The alpha-error will be set to 0.05. The analyses will be done using GraphPad Prism. Animal sample size: To detect a difference between the two groups with a 95% CI, assuming an estimated standard deviation of 20% for behavioral tests and a 20% procedural mortality, we will need 12 mice per group.

9. Risks and benefits for participants in the study

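### Per-domain cognitive recovery is assigned to Cochran-Armitage, an independent-groups test; if its levels are visits V1–V3 of the same patients, positively correlated, the test is conservative and loses power

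*Protocol*

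**What the plan says.** Protocol section 8.2 takes "The global tendency of recovery of cognitive deficits in NMDARe", defined through the proportion of patients relative to the general population, and says that this proportion "in each domain) will be assessed with the Cochran-Armitage test for trend". It names neither the ordered variable nor the sample. The same sentence continues: "other comparisons within NMDARe will be done with Wilcoxon signed-rank and McNemar's tests".

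The other relevant statements are these:

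- Section 7, on presential visits: "This study includes a total of 3 presential visits during 1 year". These are V1 at baseline, V2 at 6 months and V3 at 12 months, in the same patients.
- Section 5, on the course expected from the pilot study: "all patients at V1 have cognitive and psychiatric alterations and most still have residual deficits at V3".
- Section 4.1 classes the neurocognitive assessment as primary: "primary variables): general neurological examination and a battery of 16 tests", covering 8 domains.
- Section 8.1 sets 20 new patients and 20 pilot patients, with no sample size estimation.
- Section 8.2 also fits linear mixed models to the cognitive and psychiatric variables, between and within groups. All tests are two-sided at 5%.

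**The concern.** Cochran-Armitage compares proportions across ordered groups made up of different people. Recovery is change over time, and this study observes it in the same patients at three visits. The word that opens the next clause of the sentence in 8.2 (other comparisons) places the trend test among the within-NMDARe comparisons, and its companions there are paired tests. No other ordered variable in 8.2 fits recovery.

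On that reading the test ignores the pairing. A patient impaired in a domain at V1 is more likely than others to be impaired at V3, so the independent-groups variance is too large and the test rejects too seldom. With 20 patients per group, the likely error is to miss a real fall in the proportion impaired in a domain. The background section makes this relevant: it reports that in the pilot study the cognitive deficits "improved initially but stagnated at ~6 months", and a plateau of that kind leaves little trend to detect. Section 7 describes the same course as follows: "a slow progressive cognitive improvement occurred in most patients during the 1 year follow-up".

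**Working it through.** **Inputs from the protocol.** Three visits, n = 20 new patients, two-sided 5%, one test per domain. The protocol states no power, effect size, deficit rate or correlation for this test, so there is no figure to reproduce. Rates and correlations below are assumptions, shown as ranges.

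**Why the variance is wrong.** Let Y1 and Y3 be impairment (0/1) at V1 and V3, with visit scores −1, 0, 1. The trend statistic is T = Σ(Y3 − Y1). With constant rate p and q = 1 − p:

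- variance used by Cochran-Armitage: 2npq
- true variance in the same patients: n(pq + pq − 2·cov) = 2npq(1 − ρ), where ρ is the V1–V3 correlation of the binary outcome
- true size = 2[1 − Φ(1.96/√(1 − ρ))]

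This gives 5.0% at ρ = 0, 2.8% at 0.2, 1.9% at 0.3, 0.6% at 0.5 and 0.03% at 0.7. A negative ρ reverses the direction (6.2% at −0.1), but negative correlation of impairment within a patient is not expected.

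**Link to latent correlation.** For a rate of 50% and latent normal correlation r between V1 and V3, ρ = (2/π)·arcsin(r).

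| Latent correlation | Structure | r (V1–V3) | ρ | Size by formula |
|---|---|---|---|---|
| 0.2 | exchangeable | 0.20 | 0.128 | 3.6% |
| 0.5 | exchangeable | 0.50 | 0.333 | 1.6% |
| 0.8 | exchangeable | 0.80 | 0.590 | 0.2% |
| 0.2 | AR(1) | 0.04 | 0.025 | 4.7% |
| 0.5 | AR(1) | 0.25 | 0.161 | 3.2% |
| 0.8 | AR(1) | 0.64 | 0.442 | 0.9% |

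**Simulated size.** With n = 20 and constant rates of 30% and 50%, size at latent correlation 0.2/0.5/0.8 is about 3–4 / 1.4–2.1 / 0.2–0.4% (exchangeable) and about 4–5 / 3–4 / 1% (AR(1)). This agrees with the formula.

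**Comparator for power.** With b and c the numbers of patients changing in each direction between V1 and V3, T² = (b − c)² and the robust within-patient variance is Σ(Y3 − Y1)² = b + c. With complete data and equally spaced scores, the robust score trend test is therefore large-sample McNemar on V1–V3.

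**Simulated power, n = 20, assumed fall 70/55/45%, latent correlation 0.2/0.5/0.8:**

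| Structure | Cochran-Armitage | McNemar V1–V3, large-sample | Gain, points |
|---|---|---|---|
| Exchangeable | 33 / 31 / 28% | 36 / 44 / 63% | 3 / 13 / 35 |
| AR(1) | 33 / 33 / 30% | 32 / 37 / 51% | −1 / 4 / 21 |

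Exact McNemar recovers much less: 26/30/36% (exchangeable).

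**Other assumed patterns.** These use exchangeable correlation only, against a patient-stratified Mantel trend test, which holds its size in that case.

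- Plateau 70/50/50%, n = 20: 21/19/14% against 27/32/46%.
- Larger fall 80/60/40%, n = 20: 76/79/81% against 81/89/97%.
- Fall 70/55/45%, n = 40 (if pilot patients are included with three visits each): 65/67/69% against 67/79/93%.

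**Do the alternatives hold 5%?** The patient-stratified Mantel test has size 4.7–5.2% under exchangeable correlation at n = 20. Under AR(1) it is 5.6–6.1 / 6.6–6.7 / 7.6–7.9% at latent 0.2/0.5/0.8, and n = 40 does not cure it (5.5 / 6.9–7.0 / 7.5–7.7%). The robust score test stays at 3.8–4.9% under AR(1), with adjacent binary correlations of 0 to 0.7. Logistic GEE at n = 20 under exchangeable correlation has size 4.4–7.3% with the uncorrected sandwich variance and 3.8–5.3% with the Mancl-DeRouen correction. The corrected form has power 36/45/63% for the 70/55/45% fall.

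**The case against.** **The levels are not stated.** This is true, and the point is conditional on them. The sentence also speaks of a global tendency; if the domains were pooled, the direction could reverse. With 8 domains and assumed shared same-visit effects, size ran from 3% to 19%. The words on each domain favour separate tests, so conservatism is the better reading, but it needs three conditions: visits as levels, one test per domain, and positive correlation.

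**The detail belongs in an analysis plan.** Pairs, scores and working correlation may be left there, and their absence is not the point. The protocol does, however, commit to a named test, and on the natural reading that test does not fit the data.

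**Other analyses cover it.** Largely so. The mixed models handle repeated measures on the cognitive variables, and McNemar on V1–V3 in its large-sample form would recover the loss. But 8.2 does not assign the mixed models to the proportion impaired, and it states neither the pairs nor the form of McNemar.

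**The loss can be made to look larger than it is.** Against the stratified Mantel test it reaches about 39 points at n = 20 over the assumed falls. That figure needs exchangeable correlation of 0.8. If correlation decays over visits six months apart, that comparator is itself liberal, and the valid gap for the 70/55/45% fall is about 21 points at most.

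**A reader might infer false claims of recovery, or a compromised assessment of the rehabilitation programme.** The protocol supports neither. On the natural reading the error makes false positives rarer, and the comparison of new with pilot patients is made with the mixed models.

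**Conclusion.** The point holds in limited form. Section 8.2 assigns an independent-groups trend test to what is most naturally a repeated proportion in the same patients. Run per domain with positive within-patient correlation, it is conservative.

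For the assumed 70/55/45% fall at n = 20, the power loss against a valid within-patient comparison runs from none at low correlation to about 20–35 points at high correlation (21 under AR(1), 35 under exchangeable). Rates, falls and correlations are all assumed, and the simulations take complete data at three visits. The weight is moderate: the test is a supplementary look at domains of a primary variable, and the mixed models carry the main longitudinal analysis. It is worth correcting because a non-significant trend in a domain could be read as no recovery when the test had little chance of showing it.

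**What to change.** In section 8.2, name visit (V1, V2, V3) as the ordered variable and state the sample: new patients only, or also pilot patients and which of their visits. Replace Cochran-Armitage with a robust within-patient trend test run per domain, such as a logistic GEE with visit as a linear score and a Mancl-DeRouen small-sample variance correction. The corrected GEE was checked here only under exchangeable correlation; the robust score version of the test also held its size under AR(1). The uncorrected sandwich variance should not be used at this sample size.

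The patient-stratified Mantel/CMH trend test is an obvious alternative but should not be the first choice, because its size rises to about 6–8% when correlation decays with time. If McNemar is kept alongside, state the visit pair and whether the large-sample or exact form applies.

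The cost is one sentence in the protocol and slightly more analysis work, with no new data or visits.

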- 3.1 Memory and behavioral tests for mice (primary variables)
- 3.2 Surface clusters of NMDARs on sections of cortex/hippocampus (primary variables)
- 3.3 Hippocampal long-term (LTP) and short-term potentiation (STP) (secondary variables)

3.4 Immune/inflammatory signaling-target gene expression pathways (secondary variables): will include genes of B cell activation/function (CCL19, CxCL13, BAFF, APRIL, SYK, TACI, BAFFR, BCMA, CD40), T ell activation/function (CLDN1, IL23A, CTLA4, ICOS, ICOSLG, PDCD1, PDCD1LG2, CD40LG), TH17 signaling (IL17A, IL17RA), IL1 signaling (IL1RN, IL1B, IL1R1), IL2 signaling (IL21, IL21R), IL6 signaling (IL6, IL6R), other cytokine signaling (CXCL3, CXCL8, CX3CL1, IL12B, TNFAIP3), type 1 interferon signaling (IFI27, IFI44, IFI44L, ISG15, RSAD2, SIGLEC1), housekeeping genes (ALAS1, HPRT1, TBP, TUBB).

5 Design of the study

Human studies

This is a prospective single center, single arm, national study of 3 years duration.

The study will be conducted following the protocol that we developed for a previous prospective longitudinal observational study that was performed between 2017 and 2021 with patients with anti-NMDAR encephalitis during the post-acute stage, and that was approved by the CEIm of HCB (Study title: "Immune-mediated diseases of the synapse: symptoms, brain networks, and the link to human memory"; PI: [name]; Code: HCB/2016/0596). We will perform the exact same protocol with 3 main novelties: (1) we include five remote online study visits (clinical assessments and tasks using portable devices); (2) patients will undergo a cognitive rehabilitation program, and (3) they will have two CSF studies, as detailed below.

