Mice C57BL/6J, 8-10 weeks old will be used. Three experimental groups will be established according to 3 treatment approaches. All mice will be immunized twice (days 0 and 28) with a GluN1 peptide (amino acids 356-385) that contains the main epitope region of NMDARe. As adjuvant, we will use Addavax+Pertussis toxin that primes B cell and antibody responses with better tolerability than Freund's adjuvant. This approach results in very high titers of NMDAR antibodies with reactivity similar to those of patients (Fig 6 a,b). The corresponding 3 control groups will receive only Addavax+Pertussis toxin without peptide.

B.1. Behavioral studies

From baseline (pre-immunization) until day 71 (euthanized), animals will be regularly tested with memory/behavioral paradigms, as reported in our model of passive transfer of antibodies.[6]

B.2. Effects on NMDAR

The antibody effects will be determined in subsets of mice euthanized at day 42 (acute stage) and the rest of mice on day 71 (post-acute stage) (Fig 8). Sections of cortex/hippocampus will be examined using (1) confocal microscopy and IMARIS software to quantify the surface clusters of NMDARs, and (2) electrophysiology to assess hippocampal long-term (LTP) and short-term potentiation (STP). These techniques were described in detail in our passive immunization model [6,23] and STP in [8].

B.3. Treatment approaches to the post-acute stage

After immunization, 3 subsets of mice (and corresponding controls) will be established: not treated; treated with a mouse anti-CD20 [29] (Biogen Idec; analogous to rituximab); or treated with the anti-CD20 and a NMDAR positive allosteric modulator (SGE-301) [23]. All groups will be regularly tested with the indicated behavioral panels; on day 71 animals will be euthanized for brain confocal microscopy, LTP/STP, and studies listed below (3.5).

B.4. Immune cells and immune-inflammatory pathways

From tissue samples obtained on days 42 and 71, immune/inflammatory cells (B, T, activated microglia, etc.) will be examined by immunohistochemistry.[4,6] RNA will be extracted from brain for RNA/NanoString analysis targeting the same genes as described in patients, with mouse-RNA primers. Findings from the acute (day 42) and post-acute (day 71) stages will be compared.

8. Statistics

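### Repeated mouse behaviour tests, a primary variable, are analysed by a double ANOVA with no baseline covariate, although a pre-immunisation baseline is collected: avoidable loss of power, not bias

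*Protocol*

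**What the plan says.** Section 4.1, item 3.1, lists "Memory and behavioral tests for mice (primary variables") under objective 3. Section 7, B.1, sets the schedule: "From baseline (pre-immunization) until day 71 (euthanized), animals will be regularly tested with memory/behavioral paradigms". Immunisation is on days 0 and 28; day 42 is called the acute stage and day 71 the post-acute stage.

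Section 8.2 chooses the analysis: "For animal behavior studies with multiple determinations in time (e.g., new object recognition) we will use the double variance analysis (ANOVA"). Behaviour tests with a single determination get a simple ANOVA and are outside this point. It adds "In all experiments, the post-hoc analysis will use the Bonferroni correction for multiple tests", names GraphPad Prism as software, and gives the group size: "assuming an estimated standard deviation of 20% for behavioral tests and a 20% procedural mortality, we will need 12 mice per group".

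No covariate is named for the mouse analyses. The section does not name the two ANOVA factors, does not say where the baseline test enters, and does not say which term carries the conclusion. For the human models the same section does list adjustment variables.

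**The concern.** Section 8.2 separates tests by whether they have several determinations in time or one, so group and time are the natural two factors and the pre-immunisation test is the first level of time. On that reading:

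- The group main effect averages in a test at which no effect of immunisation or treatment can exist.
- The group-by-time interaction uses baseline as a within-mouse reference, but spreads a sustained difference over k degrees of freedom.
- The post-hoc comparisons at each time make no use of the mouse's own baseline.

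With about 10 surviving mice per group, chance baseline differences are not negligible. A real effect of immunisation, of anti-CD20 or of SGE-301 on a primary variable is then more likely to be missed, although the data that would sharpen the comparison are already being collected.

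**Working it through.** **Inputs from the protocol.** 12 mice per group, SD 20%, procedural mortality 20%, alpha 0.05 (taken as two-sided). Survivors: 12 × 0.8 = 9.6, about 10 per group.

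**The plan's own figure.** The sample-size sentence gives no difference and no power, only "To detect a difference between the two groups with a 95% CI". With n = 2(1.96 + 0.84)²/(difference/SD)², a difference of 1.35 to 1.4 SD (27 to 28 points) at 80% power gives n = 9, and 9/0.8 = 11.25, rounded up to 12. Other pairs of difference and power also give 12, so the figure is neither confirmed nor refuted, and it says nothing about the role of baseline.

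**Assumptions for the comparison.** Two groups of n = 10; SD 1; equal correlation ρ between tests; k post-baseline tests; a correct mouse-level error term. Power is from the noncentral F distribution with noncentrality λ.

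**Sustained effect of 1 SD (20 points), k = 3, ρ = 0.5**

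- Main effect with baseline as a time level: effect 3/4 = 0.75; variance of a mouse mean (1 + 3 × 0.5)/4 = 0.625; λ = 5 × 0.75²/0.625 = 4.5; df 1 and 18; power 52%.
- Interaction: sum of squared centred effects 0.75; λ = 5 × 0.75/(1 − 0.5) = 7.5; df 3 and 54; power 59%.
- Post-baseline mean, baseline dropped: variance (1 + 2 × 0.5)/3 = 0.667; λ = 5/0.667 = 7.5; df 1 and 18; power 74%.
- Post-baseline mean, baseline as covariate: variance 0.667 − 0.5² = 0.417; λ = (5/0.417) × (1 − 1/17) = 11.3; df 1 and 17; power 89%.

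About 22 of the 37 points between 52% and 89% therefore come from taking baseline out of the outcome, and 15 from the covariate. At ρ = 0.2 the main effect, interaction and covariate analysis have 71%, 39% and 88%, and the covariate itself adds only about 1 point over dropping baseline. Simulation with 4,000 runs agreed (51%, 59% and 89% at ρ = 0.5).

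**Comparisons at one time, effect 1 SD, separate error at each time.** Without baseline, λ = 5: power 37% at 0.05/3, or 33% at 0.05/4 if baseline counts as a fourth comparison. With baseline as covariate at ρ = 0.5, λ = 5/(1 − 0.25) × 16/17 = 6.3: power 46% at 0.05/3. At ρ = 0.2 or below there is no real gain.

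**Delayed effect: 0, 0.5 and 1 SD at the three tests, ρ = 0.5**

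- Planned interaction: sum of squared centred effects 0.6875; λ = 5 × 0.6875/0.5 = 6.9; power 55%.
- One baseline-adjusted average over all three tests: effect 0.5; λ = 5 × 0.25/0.417 × 16/17 = 2.8; power 35%.

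With effects 0, 0 and 1 SD the gap widens to 59% against 18%.

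**Baseline as covariate, with time and group-by-time kept.** The joint test of group and group-by-time has about 78% power against 59% for the planned interaction under the sustained effect, and about 59% against 55% under 0, 0.5 and 1 SD (ρ = 0.5). If the effect appears only at the last test and ρ = 0.7, it is at most about 2 points below the interaction. These joint-test figures shift by a few points with the choice of denominator degrees of freedom.

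**The case against.** The strongest case against has four parts.

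- **Baseline as a time level is inferred.** The protocol never says it. Section 7 also describes the mouse work as separate, with its own animal protocol, which is not at hand. This stands: a reader might infer that the plan demotes baseline to one more time point, but the text leaves its role open. What the text does fix is the model, the post-hoc method and the software, with no covariate. Dropping baseline altogether would also forgo its information (74% against 89% in the example).
- **The dilution touches only the main effect.** Objective 3 asks about reversibility and about acute versus post-acute stages, which are questions of change over time that the interaction addresses. This stands. It would be wrong to say that the whole analysis is diluted.
- **A constant effect is doubtful here.** The second immunisation is on day 28 and treatment targets the post-acute stage, so early tests may show little. This stands, and it rules out the tempting remedy of averaging all post-immunisation tests. It does not count against a baseline-adjusted model that keeps the time course.
- **Fewer mice may reach late tests.** Subsets are euthanised at day 42, so 10 per group may be optimistic unless those mice are additional. The documents do not settle this. It affects every power figure above.

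**Conclusion.** The point holds as a matter of efficiency on a primary variable. The protocol names an analysis without a baseline covariate for tests that include a pre-immunisation baseline. If baseline is a level of time, the main effect shrinks to k/(k+1) of its size (67%, 75% and 80% for k = 2, 3 and 4), and the comparisons at each time give up precision once tests are moderately correlated. The interaction escapes the dilution but has less power than a baseline-adjusted analysis when the effect is sustained.

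A reader might infer bias or an inflated type I error; neither follows. Nor can one fixed loss be quoted. The correlation, the number of tests, the effect size and its time pattern are all assumptions here, and the time pattern decides whether an averaged covariate analysis beats the interaction or loses to it. The change is worth making because it costs little.

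**What to change.** In section 8.2, replace the sentence on repeated animal behaviour tests by:

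> For behaviour tests repeated over time, the pre-immunisation value of the same test is a covariate and only post-immunisation tests are outcomes, in a repeated-measures (mixed) model with group, time and group-by-time. Groups are compared on the baseline-adjusted means at each post-immunisation time, with Bonferroni correction.

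Do not reduce this to one average over all post-immunisation tests, because that mixes in tests made before the second immunisation or before treatment. Tests with a single determination stay as planned.

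The cost is one degree of freedom and a model fitted in R, already planned for the human data, instead of GraphPad Prism. No extra animals or tests are needed.
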